7.4.1. Outcomes and Study Continuation

Two outcomes are possible from the interim analysis: statistical significance or nonsignificance. In the event of a nonsignificant difference between ACM and CM Cycle-1 CR rates (p-value > 0.00321), the study will continue to accrue and randomize patients.

If the interim analysis result for the primary analysis of Cycle-1 CR rate (see section 7.9.1) is statistically significant (p-value ≤ 0.00321), then randomization will be stopped. Additional eligible stage-2 patients will be enrolled into the study to receive open-label ACM until the planned enrollment of 53 ACM patients is complete. No additional patients will be enrolled into the CM treatment arm. Terminating randomization after the interim analysis will have a negative effect on the power to declare treatment differences in secondary endpoints as statistically significant, however it is understood from polling investigators that they would be unwilling to enroll patients into the study once ACM has been established as superior to CM with respect to Cycle-1 CR rate.

7.5. Overall Type-1 Error Rate

A type-1 error in statistics is rejecting the null hypothesis as false when it is actually true. In this study, this corresponds to concluding the population's efficacy response following ACM is superior to that from CM when in fact it is not. The probability of committing a type-1 error is commonly referred to as the significance level or α (alpha) level. The overall significance level for this study will be 2.5% using one-sided hypothesis tests.

7.5.1. Type-1 Error Rate Control for Interim Analysis

An O'Brien-Fleming sequential design¹ is employed to maintain the overall 2.5% significance level of the study following the single interim analysis described in section 7.4. Although the interim analysis will include several safety endpoints, cycle-1 CR rate will be the only efficacy endpoint considered when determining whether O'Brien-Fleming boundaries have been crossed. Programming statements in Table 2 were run in SAS software (version 9.4) giving output in Table 3 and Table 4. Thus, according to the O'Brien-Fleming boundaries, the final analysis will use a one-sided significance level of 2.378% to determine statistical significance (see Table 4).

7.5.2. Type-1 Error Rate Control for Multiple Comparisons

Without taking appropriate measures, testing multiple efficacy parameters inflates the overall significance level since the probability of making a type-1 error in at least one from a set of hypothesis tests is greater than the probability of making a type-1 error in any single test. The hierarchical closed test procedure^{3,4} will be used to maintain the overall 2.5% significance level.

The order of efficacy endpoints for the hierarchical closed test procedure is:

1. Cycle-1 CR rate
2. Progression-Free Survival
3. Stem Cell Transplant Rate
4. Cycle-1 Combined CR Rate
5. Cycle-1 Combined Remission Rate
6. Overall Survival
7. Combined Remission Duration
8. Combined CR Duration
9. CR Duration

The final analysis will be conducted at a one-sided 2.378% significance level using the statistical procedures described below. Cycle-1 CR rate, the primary efficacy endpoint, will be declared statistically significant if its test p-value ≤ 0.02378 . A secondary efficacy endpoint will be declared statistically significant only if its test p-value ≤ 0.02378 and all efficacy endpoints preceding it in the hierarchy are statistically significant. In other words, declaration of statistical significance for efficacy endpoints will advance in order down the hierarchy only until a p-value > 0.02378 is found.

In addition, although primary and supportive analytical methods are specified for each endpoint in the hierarchy, only the p-value from the primary analysis will be used for deciding statistical significance. Supportive (sensitivity) analyses are to demonstrate the robustness of primary results to slight modifications to how endpoints are defined and/or analyzed.

Declarations of statistical significance will not be advanced for endpoints not included in the hierarchy of the closed test procedure (e.g., ECOG performance status).

It is worthwhile noting...

The testing hierarchy is not intended to represent a ranking of efficacy endpoints based solely on clinical importance. It resulted from a careful consideration balancing clinical importance, perceived regulatory acceptability, statistical power (presumed probability of treatment-arm differences achieving statistical significance), and interrelatedness of the efficacy endpoints. This study is not powered to demonstrate statistical significance of OS differences typically observed in clinical studies involving relapsed/refractory AML patients. None of this however would invalidate or undermine the extreme clinical importance of a statistically significant OS advantage for ACM over CM observed in this study.

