5. EFS
6. Stem cell transplant rate

Each efficacy endpoint will be tested at a one-sided 2.5% significance level using the statistical procedures described above. CR rate, the primary efficacy endpoint, will be declared statistically significant if its test p-value ≤ 0.025 . A secondary efficacy endpoint will be declared statistically significant only if its test p-value ≤ 0.025 and all efficacy endpoints preceding it in the hierarchy are statistically significant. In other words, declaration of statistical significance for efficacy endpoints will advance in order down the hierarchy only until a p-value > 0.025 is found.

In addition, although there will be primary and supportive analytical methods for each endpoint in the hierarchy (supportive methods will be documented in the formal Statistical Analysis Plan), only the p-value from the primary analysis will be used for deciding statistical significance. Supportive (sensitivity) analyses are to demonstrate the robustness of primary results to slight modifications to how endpoints are defined and/or analyzed.

Declarations of statistical significance will not be advanced for endpoints not included in the hierarchy of the closed test procedure.

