7.9.6. Complete Remission Duration

CR duration is defined only for patients who achieve a CR during the study and is measured from the date of CR (Day 1) until relapse.

An additional rule for defining CR duration is:

- A patient found to have relapsed after missing one or more scheduled response assessments will have his CR duration end on the scheduled date for the first missed response assessment following the last confirmation of CR

Rules for censoring CR duration are:

- A patient who dies while in remission will have his CR duration censored on the date of death
- A patient in remission on the date he is lost to follow-up will have his CR duration censored on the date of his last response assessment
- A patient in remission on the database lock will have his CR duration censored on the date of his last response assessment

Hypothesis testing for CR duration will be based on the stratified log rank test statistic (see Table 6). Stratification levels will be the same as those used for the randomization scheme (see section 6). Two Cox PH models will be fit to provide estimates of the HR. One model will include treatment arm as the only independent variable, and the second

model will include treatment arm and the stratification factors used for randomization. KM “survival” curves will be graphed for visual inspection of differences in CR duration between the treatment arms. Within–treatment-arm statistics will include the number and percentage of patients who achieve a CR, the number and percentage of censored CR durations, quartile CR durations, 95% CIs for the quartile CR durations, and KM “survival” percentages with 95% CIs at select milestone times (e.g., 6, 12 and 18 months). Between–treatment-arm statistics will include HRs from the Cox PH models and their 95% CIs.

Sensitivity analyses will be run with CR duration censored on the date of BM or PBSC transplant.

If the test for between–treatment-arm homogeneity of any baseline characteristic gives two-sided p-value <0.10, then the effect that baseline characteristic has on CR duration will be quantified using Cox PH modeling. Two PH models will be fit. One model will include the baseline characteristic in question as the only independent variable, and the second model will include the baseline characteristic and the stratification factors used for randomization.

Two endpoints analogous to CR duration will be analyzed using similar methods.

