- Combined CR Duration (defined only for patients who achieve a combined CR during the study): time from the earliest date of combined CR (Day 1) until relapse after combined CR
- Combined Remission Duration (defined only for patients who achieve combined remission during the study): time from the earliest date of combined remission (Day 1) until relapse after combined remission

Response categories included in “combined CR” and “combined remission” are delineated in Section 3.

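### The SAP puts three responder-only remission durations at steps 7-9 of its confirmatory hierarchy; these are not randomised comparisons and can mislead in either direction, though a formal claim on them is unlikely to be reached

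*SAP*

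**What the plan says.** - **Hierarchy.** SAP 7.5.2 sets a nine-step hierarchical closed test. Step 7 is "7. Combined Remission Duration", step 8 Combined CR Duration and step 9 CR Duration. A secondary endpoint is declared significant "only if its test p-value ≤ 0.02378 and all efficacy endpoints preceding it in the hierarchy are statistically significant".
- **Who has a value.** SAP 7.9.6: "CR duration is defined only for patients who achieve a CR during the study and is measured from the date of CR". The companion endpoints follow the same pattern, for example "Combined Remission Duration (defined only for patients who achieve combined remission during the study". The window is the whole study, not cycle 1.
- **Test.** "Hypothesis testing for CR duration will be based on the stratified log rank test statistic". SAP Table 6 files this under the ITT population as the primary analysis.
- **Deaths.** "A patient who dies while in remission will have his CR duration censored on the date of death".
- **Crossover.** SAP 7.1 groups ITT patients by randomised arm. Its per-protocol rule for treatment received makes an exception for crossover ACM, so those patients stay in CM there too. SAP 7.9.1 rejects best response over the whole study as the primary endpoint because crossover would confound it.
- **OS.** SAP 7.5.2 places OS at step 6 and, in its closing remarks, says the study is not powered for typical OS differences.
- **Protocol.** The hierarchy in Protocol 11.4.2 has six steps, ends with "6. Stem cell transplant rate" and contains no duration endpoint. The SAP (section 4) is written to Amendment 7; Protocol 2.7 describes Amendment 11.

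**The concern.** Randomisation makes the arms comparable as randomised. It does not make the responders in each arm comparable when treatment changes who responds. If ACM turns some patients into responders who would have failed on CM, the ACM responder group contains a kind of patient that the CM group lacks. A log-rank difference between the groups can then come from case mix alone. If the extra responders relapse early, ACM looks worse; if they relapse late, ACM looks better.

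Crossover adds a second fault. A CM failure who reaches CR on crossover ACM enters the CM duration set, so part of that set measures alvocidib. The SAP guards its primary endpoint against this by using cycle-1 response, but not steps 7 to 9.

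What is at stake is the meaning of a formal claim. SAP 7.5 frames the error to be controlled as wrongly concluding that the population's response to ACM is superior. A contrast among responders cannot answer that question, whatever its p-value.

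**Working it through.** **1. Plan figures.** A two-look O'Brien-Fleming design at information fraction 56/106, one-sided 0.025, gives nominal levels of 0.003206 and 0.023779 (SAP: 0.00321 and 0.02378). Maximum information is 117.75. Total N = 2 × 117.75 × (0.7 × 0.3 + 0.4 × 0.6) = 105.97, so 106. The SAP's figures reproduce.

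**2. Who has a CR duration, by expected cycle-1 CR.**
- SAP (53 per arm, 70% vs 40%): 53 × 0.7 = 37.1 ACM and 53 × 0.4 = 21.2 CM, about 58 of 106. About 48 have none: 30% of ACM and 60% of CM.
- Protocol 11.2.2 (28 per arm, 70% vs 30%): 19.6 and 8.4, so 28 of 56 have none.
- Fewer are missing for the combined endpoints, which also count CRi and CRp, and PR for combined remission.

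**3. Crossover share of the CM set.** Assume that 30% to 70% of CM patients without a cycle-1 CR reach CR after crossover. Non-CR patients: 53 − 21.2 = 31.8.
- 30%: 9.54 / (21.2 + 9.54) = 31%.
- 70%: 22.26 / (21.2 + 22.26) = 51%.

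**4. Bias against ACM.** Assumptions: treatment changes no patient's remission length; no crossover remissions; exponential relapse; 24-month censoring (two-year follow-up, Protocol 5.6); median 12 months for patients who respond to either regimen and 6 months for those who respond only to ACM.
- Hazards: ln2/12 = 0.0578 and ln2/6 = 0.1155 per month.
- Relapsed by 24 months: 1 − 2⁻² = 0.75 and 1 − 2⁻⁴ = 0.9375.
- Mean time at risk: 0.75/0.0578 = 12.98 and 0.9375/0.1155 = 8.12 months.
- At 70% vs 40%, the ACM responder mix is 4/7 and 3/7. Rate = (4/7 × 0.75 + 3/7 × 0.9375) / (4/7 × 12.98 + 3/7 × 8.12) = 0.830/10.90 = 0.0762. Ratio to CM: 0.0762/0.0578 = **1.32**.
- At 70% vs 30%, the mix is 3/7 and 4/7. Rate = 0.857/10.20 = 0.0840; ratio about **1.45**.
- If half of the ACM-only type in the CM arm reach remission after crossover (70% vs 40%), the CM mix is 0.40 to 0.15. The CM rate is 0.801/11.66 = 0.0687 and the ratio falls to 1.11. If all do, it is 1.00.

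**5. Chance of a nominally significant result.** Simulation of 10,000 trials per row: 53 per arm, 70% vs 40%, one-sided 0.02378, unstratified log-rank on responders, 24-month censoring, no effect on any patient's duration. Patients who respond to either regimen have an assumed median of 8 months.

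| Median of ACM-only responders, months (assumed) | Falsely favours ACM | Falsely favours CM |
|---|---|---|
| 2 | <0.1% | 26% |
| 4 | 0.3% | 13% |
| 8 (no selection) | 3.4% | 2.2% |
| 16 | 18% | 0.1% |
| 24 | 33% | <0.1% |

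The 3.4% in the neutral row is small-sample error of the log-rank test. At 28 per arm, 70% vs 30%, one-sided 0.025, the rows for 16 and 24 months give 17% and 28% favouring ACM; those for 4 and 2 months give 11% and 22% favouring CM.

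**6. Censoring deaths in remission.** A separate simulation set CR at 70% in both arms, to isolate the censoring, with the same relapse risk in both. Half of responders were frail, with four times the relapse hazard of the rest, and early deaths in remission occurred only among frail ACM responders. With such deaths in 0%, 30% or 60% of them (assumed), false ACM wins were 2.4%, 4.3% and 8.9%.

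**The case against.** **Reach is small.** A duration can be declared only after six earlier successes, including PFS and OS on all randomised patients, and the SAP says OS is not powered. The durations have little power themselves: even if all 58 expected responders relapse, power at an assumed hazard ratio of 0.6 is about 46%. This stands and lowers the priority.

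**The two mechanisms can offset.** Crossover remissions in the CM arm pull the 1.32 toward 1, so it is a no-crossover illustration and not an expected value. This stands.

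**The bias against ACM cannot produce a false claim.** Tests are one-sided for ACM, so that scenario costs a missed or adverse-looking result. This also stands; the false-claim risk comes only from the opposite case.

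**Stronger readings that the documents do not support.**
- A reader might infer that most patients would have no duration. At the SAP's rates about 58 of 106 would have one, and at the protocol's exactly half. The problem is the unequal exclusion by arm.
- A reader might infer that the trial's type-1 error is inflated. Nothing at steps 7 to 9 can affect steps 1 to 6. The fixed sequence also holds its level for the narrow hypothesis of equal durations among observed responders, apart from small-sample error. The fault lies in what is being estimated.

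**Reconciliation may settle it.** The SAP says later amendments will be reviewed for changes to it, and adopting the current protocol order removes the three steps. That supports the fix, but the SAP as it stands still contains them.

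**Conclusion.** The point holds, with limited practical reach. Steps 7 to 9 attach formal significance to comparisons among patients selected by response, with 30% of ACM and 60% of CM patients expected to have no CR duration at the SAP's rates, and with crossover-ACM remissions credited to CM.

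The direction of bias is not known in advance. The illustrations run from a relapse-rate ratio of about 1.32 against ACM (about 1.45 at the protocol's rates) to an 18% to 33% chance of a nominally significant result falsely favouring ACM. Both ends rest on assumed remission medians, because the documents give no duration figures for this design, and both assume no crossover remissions. The 18% to 33% describes the duration test taken alone; the chance of a false declaration in the trial is lower, because all six earlier steps must succeed first.

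Priority lies between minor and should-fix: the defect is clear and cheap to remove, but it does not touch the primary endpoint or the claims most likely to be made.

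**What to change.** - Delete steps 7 to 9 from the hierarchy in SAP 7.5.2. On this point that matches Protocol 11.4.2; the rest of the two orders still has to be reconciled.
- In SAP 7.9.6 and Table 6, drop hypothesis testing for the three durations. Report them descriptively by arm for remissions reached on randomised treatment, and show remissions reached after crossover separately.
- Treat death in remission as a competing event and report cumulative incidence of relapse, instead of censoring at death.
- Keep formal time-to-event tests on endpoints defined for every randomised patient (OS, and EFS or PFS once the documents agree).

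The cost is SAP wording and three formal claims at the end of the order that were unlikely to be reached. No sample-size change follows.

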7.6. Patient Disposition

The numbers of patients randomized (ITT population), dosed (safety population) and included in the response-available, per-protocol and crossover populations will be summarized by frequency counts within treatment arm. Time on study will be summarized as a continuous variable within treatment arm (mean, standard deviation, median, minimum and maximum values). Reasons for discontinuation will be summarized within treatment arm as a categorical variable (number and percentage of patients in each category). Relevant data supporting these summaries will be listed by patient within treatment arm.

7.7. Baseline Characteristics

Patient age in years on the date of randomization will be calculated by dividing the number of days since birth (Day 1) by 365.25. If body surface area (BSA) expressed in m² is missing in the study database, then it will be calculated using the formula⁵

$$BSA = \sqrt{\frac{W \times H}{3600}}$$

where W is the patient's weight in kg and H is the patient's height in cm.

Summaries of baseline characteristics will include within- and between-treatment-arm descriptive statistics appropriate for continuous, time-to-event and categorical variables (see section 7). Separate summaries will be produced for the ITT, safety, response-available, per-protocol and crossover patient populations. The Student t test (continuous variables), the log rank test (time-to-event variables), or the Fisher exact test (categorical variables) will be used to quantify the effectiveness of randomization to create similar distributions of these variables between treatment arms. The effect any baseline characteristic with two-sided p -value <0.10 has on efficacy outcomes will be investigated (see sections 7.9.1 through 7.9.6).

Baseline characteristics include demographic data (e.g., age, sex, race, ethnicity, height, weight and BSA); AML history (e.g., clinical onset of AML [de novo AML, prior MDS or prior leukemogenic therapy], time since AML diagnosis, peripheral blood and bone marrow blast percentages, cytogenetic risk group, frontline AML therapy and response to frontline AML therapy [see section 6]); MCL-1 dependence; and other

medical history (e.g., baseline ECOG performance status, hemoglobin, leukocyte and platelet counts, and blood chemistry parameters assessing liver and kidney function). Reported medical history terms will be mapped to Medical Dictionary for Regulatory Activities (MedDRA) preferred terminology and then summarized within and between treatment-arms by incidence rates for each MedDRA primary system organ class (SOC) and preferred term (PT). Optionally, depending on the perceived relevance, prestudy medications will be mapped to terminology in the World Health Organization (WHO) Drug Dictionary Enhanced (DDE) and then summarized within treatment arm by usage rates for each WHO DDE anatomical and therapeutic class (ATC) and preferred (i.e., standardized) drug name. Relevant data supporting these summaries will be listed by patient within treatment arm.

7.8. Study Drug Exposure

Patients' total exposures to study drugs and average exposures per treatment cycle will be calculated and summarized within treatment arm by the mean, standard deviation, median, minimum and maximum values. Numbers of treatment cycles received will be summarized within treatment arm as a continuous variable (by the mean, standard deviation, median, minimum and maximum values) and as a categorical variable (by the number and percentage of patients in each category). Reasons for noncompliance with protocol-specified dosing schedules will be summarized within treatment arm as a categorical variable. Relevant data supporting these summaries (including actual infusion durations and expected doses based on BSA calculated from a patient's latest reported height and weight) will be listed by patient within treatment arm.

7.9. Efficacy Endpoints

Relevant data supporting efficacy analyses will be listed by patient within treatment arm.

7.9.1. Remission Rates

The primary efficacy endpoint is cycle-1 CR rate (i.e., the percentage of patients who achieve a CR after one cycle of treatment). Cycle 1 does not end until the patient starts cycle 2 or alternative AML therapy other than supportive measures (e.g., blood product transfusions). Therefore, a patient whose first response assessment in cycle 1 is a CRi or CRp* is considered to have achieved CR if neutrophils and platelets recover prior to initiation of cycle 2 or alternative AML therapy including bone marrow or stem cell transplant. Patients who, for any reason, do not supply bone marrow for response assessment are counted among those not achieving remission. Best response during the study (i.e., best response following one or more cycles of treatment) was not selected as the primary efficacy endpoint due to the anticipated confounding effects of patients who are randomized to CM but crossover after one or two cycles to receive treatment with ACM.

Three response assessments are planned for each postbaseline bone marrow sample:

1. The "central review" performed by a panel of independent, expert hematologists according to an approved charter under change control

* See footnote on page 6.

2. The “local review” of bone marrow and blood test results by the investigator at the study center where patient is enrolled
3. The “sponsor review” by employees and/or agents of Tolero Pharmaceuticals

It is beyond the scope of this SAP to restate or summarize the written charter detailing the methods and criteria the panel of hematologists use to grade response, but both central and local assessments are made according to criteria specified in the study protocol. The primary assessments of remission for comparing efficacy across treatment arms is the central review of bone marrow; however, in cases where the central hematologists are unable to rate response, the investigator’s response assessment will be used in place of the missing central assessment. Supportive efficacy analyses will be conducted using assessments from the local and sponsor reviews.

Hypothesis testing will be based on the stratified Cochran-Mantel-Haenszel (CMH) general association test statistic^{6,7} (see Table 5). Stratification levels will be the same as those used for the randomization scheme (see section 6). Although the alternative hypothesis for the CMH general association test statistic is that cycle-1 CR is correlated with treatment arm in at least one stratum, the statistic has low power for detecting an association in which the patterns of association for some of the strata are in the opposite direction of the patterns displayed by other strata.⁸ Therefore, a statistically significant CMH general association statistic will validate the positive contribution of alvocidib (added to CM) to induce CR (over CM alone).

Within–treatment-arm statistics will include the number and percentage of patients rated as not achieving CR due to not providing a bone marrow biopsy/aspirate, proportion of patients who achieve a cycle-1 CR and exact 95% CI estimated without stratification. Between–treatment-arm statistics will include the Mantel-Haenszel odds ratio and 95% CI estimated with stratification.

A standard logistic regression (LR) model will be estimated relating the probability of a cycle-1 CR as a function of baseline MCL-1 dependence, treatment arm, and the two-way interaction between baseline MCL-1 dependence and treatment arm. If the p-value for the Wald chi-square statistic for two-way interaction is >0.10, then the Wald chi-square statistic for treatment arm will be interpreted as testing the equality of cycle-1 CR rates controlling for the effect of baseline MCL-1 dependence. Results will be presented graphically as follows. Patients will be divided into groups according to which range of values their baseline MCL-1 dependence falls:

$$(0\%-\leq d_1), (d_1-\leq d_2), (d_2-\leq d_3), \dots, (d_8-\leq d_9), (d_9-100\%)$$

where d_1, \dots, d_9 are deciles for baseline MCL-1 dependence regardless of treatment arm. Empirical within–treatment-arm cycle-1 CR rates will be calculated for patients within each range and plotted alongside cycle-1 CR probabilities estimated from the LR model.

Table 5. Statistical Analyses of Cycle-1 CR Rates

Analysis Population	Analytical Method	Response Assessment	Role of Analysis
Intent-to-Treat	Stratified CMH	Central	Primary
Intent-to-Treat	Stratified CMH	Local and Sponsor	Supportive

Table 5. Statistical Analyses of Cycle-1 CR Rates

Analysis Population	Analytical Method	Response Assessment	Role of Analysis
Intent-to-Treat	Logistic regression	Central	Supportive
Intent-to-Treat	Logistic regression	Local and Sponsor	Supportive
Per-Protocol	Stratified CMH	Central	Supportive
Per-Protocol	Stratified CMH	Local and Sponsor	Supportive
Per-Protocol	Logistic regression	Central	Supportive
Per-Protocol	Logistic regression	Local and Sponsor	Supportive
Response-Available	Logistic regression	Central	Supportive
Response-Available	Logistic regression	Local and Sponsor	Supportive
Subgroups based on patient characteristics	Logistic regression	Central, Local and Sponsor	Exploratory

If the test for between-treatment-arm homogeneity of any baseline characteristic gives two-sided p-value <0.10, then the effect that baseline characteristic has on cycle-1 CR rate will be quantified using LR. Two LR models will be fit. One model will include the baseline characteristic in question as the only independent variable, and the second model will include the baseline characteristic and the stratification factors used for randomization.

Other remission rates (e.g., cycle-1 combined CR rate and cycle-1 combined remission rate) will be summarized similar to cycle-1 CR rate.

Correlation between central and local review will be assessed descriptively in 2-way frequency tables, both as a bivariate response (CR yes or no) and on the full scale (CR, CRi, CRp, PR, resistance/relapse). The simple kappa coefficient^{8,9} will be calculated as a measure of agreement between the central and local reviews. Since the two response variables are two independent ratings of the same tissue sample, the kappa coefficient equals 1 when there is complete agreement of the raters. When the observed agreement exceeds chance agreement, kappa is positive, with its magnitude reflecting the strength of agreement. Although this is unusual in practice, kappa is negative when the observed agreement is less than chance agreement.⁸

